4.2. Secondary objectives

- To compare the safety and tolerability of ACTs and TACTs within and across sites and regions, including comparisons of 'non-matching' ACTs vs TACTs (AL+PBO versus ASMQ+PPQ, ASMQ+PBO versus AL+AQ).
- To compare additional measures of treatment efficacy between treatment arms, including the 63-day ACPR, the post-treatment prophylactic effect of ACTs and TACTs defined as the 42-day and 63-day PCR uncorrected ACPR, gametocyte carriage, parasite clearance rates and fever clearance.
- To assess pharmacokinetic and pharmacodynamic interactions between antimalarials in TACTs

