## STATISTICAL ANALYSIS PLAN

### 1. Analysis Considerations

#### 1.1 General Analysis Approach

The main analysis strategy for the primary outcome will be the intention-to-treat (ITT) principle. In this analysis, patients will be analysed according to the arm of randomisation irrespective of the treatment that was actually given. Complete Case Analysis will be used in the ITT analysis population (Groenwold et al 2012; Mukaka et al 2016; Sullivan et al 2018). Furthermore, the estimates of efficacy using survival analysis will be done. This approach will help in handling missing data as all patients will be included in the analysis and censored at their last follow-up time. These ITT analyses will be followed by the per protocol (PP) analysis. In this analysis only those that adhered to the protocol with respect to the primary outcome will be included for analysis of the primary outcome.

Key secondary endpoints such as parasite clearance parameters (e.g. half-lives), safety and tolerability data will be analysed similar to the ITT approach for the main primary outcome. In this analysis, patients will be analysed according to the arm of randomisation irrespective of the treatment that was actually given and all patients will be included in the analyses irrespective of their follow-up status as long as they have the data. Withdrawals and losses to follow up will not affect the analyses of this data as long as the relevant data needed for these analyses is available prior to withdrawal or loss to follow up.

Data analysis will mainly be performed using Stata 17 or higher, StataCorp, [name] or in R software.

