#### 2.1.2. Primary endpoint

42-day efficacy defined as PCR-corrected adequate clinical and parasitological response (ACPR).

*(NB, WHO definition of ACPR: absence of parasitaemia at day 42 irrespective of axillary temperature and without previously meeting any of the WHO criteria for early or late treatment failure, or late parasitological failure.)*

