***Handling of missing data***

In the ITT analysis in which efficacy will be reported as proportions of outcomes using Complete case Analysis.

In the PP analysis in which efficacy will be reported as proportions of outcomes, patients in which study drugs are discontinued and/or endpoints are not available due to other reasons (such as withdrawal from the study, loss to follow up, *P falciparum* (Pf) or *P vivax* (Pv) reinfections and inconclusive PCR correction) will be excluded from the analysis.

[figure not shown]
In the Kaplan-Meier/survival analysis subjects in which study drugs are discontinued and/or endpoints are not available due to other reasons (such as withdrawal from the study, loss to follow up, Pf or Pv reinfections and inconclusive PCR correction) will be censored or treated as competing risks, as appropriate, from the moment of occurrence of one of these events.

Similar analyses as secondary endpoints will be performed for day 63 PCR corrected efficacy and day 42 and day 63 the PCR uncorrected data as well. Where applicable, we will also report the cumulative reinfection rate. The treatment efficacy, 95% confidence intervals and p-values for the comparison of ACTs with matching TACTs will be presented as outlined in tables 2, 3, 4 and 5 below.

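### Excluding reinfected patients from PCR-corrected day-42 proportions biases the arm difference towards the arm with fewer reinfections and costs power; the Kaplan-Meier alternative is left open and is not tied to the margin

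*SAP*

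**What the plan says.** The primary endpoint is "42-day efficacy defined as PCR-corrected adequate clinical and parasitological response (ACPR"), compared between matching ACT and TACT within each site. SAP 1.1 states that "The main analysis strategy for the primary outcome will be the intention-to-treat (ITT) principle" and that "Complete Case Analysis will be used in the ITT analysis population". PP and survival analyses are also planned.

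Under Handling of missing data, SAP 3.3 gives three rules:

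- **PP proportions.** Reinfections are listed with withdrawal and loss to follow-up as reasons why an endpoint is not available. Patients with "reinfections and inconclusive PCR correction) will be excluded from the analysis".
- **ITT proportions.** Only complete-case analysis is named. The SAP does not say whether a PCR-confirmed reinfection is a success, a failure or a missing endpoint. The definition of response in SAP 2.1.2 does not settle it.
- **Survival analysis.** "Pf or Pv reinfections and inconclusive PCR correction) will be censored or treated as competing risks, as appropriate". No rule is given by type of event. SAP 1.1 mentions censoring only.

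The margin of -6 points (SAP 2.2.1) is a difference in efficacy. Table 2a reports risk differences. Table 2b gives Kaplan-Meier efficacy per arm but compares arms by hazard ratio, and the text of SAP 3.3 gives Kaplan-Meier methods a visual role.

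Protocol 4.2 lists among the secondary comparisons "the post-treatment prophylactic effect of ACTs and TACTs defined as the 42-day and 63-day PCR uncorrected ACPR".

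**The concern.** A patient reinfected on day 35 supplies 35 days of evidence that the original infection had not recrudesced. Exclusion discards that evidence but keeps every recrudescence in the numerator. The failure proportion is therefore overstated in both arms, and more so in the arm with more reinfections. Post-treatment prophylaxis is itself a planned comparison, so unequal reinfection between arms is foreseeable.

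Three things are at stake: a biased difference to set against a 6-point margin, fewer evaluable patients than the sample size assumed, and a main ITT analysis whose denominator is not fully defined. The Kaplan-Meier estimate would use the discarded follow-up, but the plan neither fixes its handling of reinfection nor gives it a role in the non-inferiority decision.

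**Working it through.** **1. The plan's own figure.** Inputs from SAP 2.2.1: ACT efficacy 96%, TACT 97-98%, margin 6 points, one-sided alpha 0.025, power about 80%, allocation 1:2. With TACT at 98% and unpooled variance:

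n(ACT) = (1.960 + 0.842)² × [0.96×0.04 + 0.98×0.02/2] / (0.02 + 0.06)² = 7.849 × 0.0482 / 0.0064 = 59.1, so 60 ACT and 120 TACT, as stated. Power at 60/120 is 80.6%. The figure reproduces only at 98%; at 97% the power is 65%. The 20% addition to 72/144 is for loss to follow-up only.

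**2. Model for the bias.** The documents give no reinfection rate, so every rate here is an assumption. Let r be the day-42 risk of recrudescence and q that of reinfection, with constant, independent hazards hr = -ln(1-r) and hq = -ln(1-q).

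- P(recrudescence first) = hr/(hr+hq) × [1 - (1-r)(1-q)]
- P(neither) = (1-r)(1-q)
- Failure with reinfections excluded = P(recrudescence first) / [P(recrudescence first) + P(neither)]
- Failure by competing-risk cumulative incidence = P(recrudescence first)
- Failure by Kaplan-Meier with reinfections censored = r

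Worked case, r = 4%, reinfection 20% ACT and 10% TACT:

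- ACT: 0.0408/(0.0408+0.2231) × 0.232 = 0.0359; 0.0359/(0.0359+0.768) = 4.46%.
- TACT: 0.0408/(0.0408+0.1054) × 0.136 = 0.0380; 0.0380/(0.0380+0.864) = 4.21%.
- Shift in TACT minus ACT efficacy: +0.25 points by exclusion; 3.59 - 3.80 = -0.21 by cumulative incidence; 0 by censoring.

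**3. Range, in percentage points of TACT minus ACT efficacy.**

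| Reinfection ACT/TACT | Exclusion, failure 4% v 4% | Cumulative incidence, 4% v 4% | Exclusion, failure 4% v 10%: shift from -6 |
|---|---|---|---|
| 10/5% | +0.11 | -0.10 | -0.03 |
| 20/10% | +0.25 | -0.21 | -0.03 |
| 30/15% | +0.44 | -0.33 | -0.01 |
| 40/20% | +0.70 | -0.45 | +0.08 |
| 50/20% | +1.22 | -0.70 | +0.59 |

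Positive values favour TACT only because these pairs give TACT fewer reinfections. In the last column, over ACT reinfection of 10-50% and TACT 5-20% with ACT never the lower, the shift runs from -0.63 (20/20%) to +1.44 (50/5%).

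Two other models agree on sign at equal efficacy. If every recrudescence is counted before any reinfection, exclusion gives +0.2 to +1.5 for 10/5% to 40/20%. If reinfection starts only when prophylaxis ends, with TACT prophylaxis assumed longer, exclusion gives about 0 to +0.7, censored Kaplan-Meier about 0, and cumulative incidence about -0.05 to -1.0.

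**4. False non-inferiority within a site.** Simulating 60/120 at 96% v 90% with an Agresti-Caffo interval and reinfected patients dropped, the one-sided error is 1.9-2.1% at 20/10%, 30/15% and 40/20%, against about 2.2% when they are kept as non-failures. A cruder normal approximation gives about 2.1-2.9% for most pairs and 3.5% at 40/10%.

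**5. Power.** At 20/10%, 60×0.8 = 48 and 120×0.9 = 108 patients remain; at 30/15%, 42 and 102. For 96% v 98%:

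- 48/108: SE = √(0.0384/48 + 0.0196/108) = 0.0313; 0.08/0.0313 - 1.96 = 0.59; power 72%.
- 42/102: SE = √(0.0384/42 + 0.0196/102) = 0.0333; 0.08/0.0333 - 1.96 = 0.45; power 67%.

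These leave out the shift in the estimate. With it included, simulated power falls from about 88% to 81% and 78% (Agresti-Caffo interval, which starts higher).

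**6. Precision of the alternative.** At 60/120 and 96% v 98%, the SD of the difference is 3.0 points by censored Kaplan-Meier and 3.3 by exclusion at 20/10%, and 3.1 v 3.6 at 30/15%. Using 0.08/0.030 - 1.96 = 0.71 and 0.08/0.031 - 1.96 = 0.62, Kaplan-Meier power is about 76% and 73%. It recovers part of the loss, not all.

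**The case against.** Exclusion is written only for PP, and the main strategy is ITT. Patients with a recurrence are followed to day 63 (Protocol 9.5.5), so later data exist, and nothing says that ITT drops them. This stands: for ITT the defect is an undefined status, with the same bias only if the PP classification carries over.

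The plan would also make unequal reinfection visible, through per-arm survival efficacy, PCR-uncorrected efficacy and, where applicable, a cumulative reinfection rate. That is true, but none of these is set against the margin. Making Kaplan-Meier the decision analysis replaces the sponsor's choice and needs independent censoring. That is a real cost, though a modest one.

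A reader might infer four stronger things that the documents do not support:

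- **That TACT is favoured.** Prophylaxis is only something to compare, and Protocol 3.1 describes elimination as reasonably well matched within each drug pair.
- **That false non-inferiority rises.** The shift towards the arm with fewer reinfections is shown at equal efficacy. At the margin it goes either way, and within-site error stays near nominal at most assumed rates.
- **That a pooled test is anti-conservative.** At 460/921 patients the error reaches about 3.7% at 30/10% and 5.8% at 40/10%, but is 2.4-2.8% at 2:1 reinfection ratios. The objective is within site, and no pooled non-inferiority test is specified.
- **That choosing between censoring and competing risks moves a large part of the margin.** The 1.9-point spread at 50/20% is exclusion (+1.2) against cumulative incidence (-0.7). The open choice itself is worth 0.1 to 0.7 points in the constant-hazard model.

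**Conclusion.** The point holds in this limited form. The PP rule gives a biased and less precise estimate of PCR-corrected efficacy, and ITT does too if it treats reinfection as a missing endpoint.

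At equal 4% recrudescence the shift is 0.1 to 1.2 of 6 margin points, towards the arm with fewer reinfections. At 4% v 10% failure it lies between about -0.6 and +1.4. The analytic loss of power is about 8 points at 20/10% reinfection and 13 at 30/15%, and it does not depend on which arm has the longer prophylaxis effect in principle, only on how many patients are dropped.

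All sizes rest on assumed reinfection rates and, for the lack of bias in Kaplan-Meier, on reinfection being independent of recrudescence. The open survival rule is a smaller matter numerically. The more important gap is that the hazard ratio in Table 2b cannot be read against -6 points. This is a worthwhile and inexpensive improvement, not a demonstrated error in the trial's conclusions.

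**What to change.** In SAP 3.3 and Table 2b:

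- Report the TACT-minus-ACT difference in Kaplan-Meier day-42 PCR-corrected efficacy with its confidence interval, censoring at reinfection or indeterminate PCR.
- Make this the non-inferiority analysis, comparing its lower limit with -6 points in the ITT and PP sets.
- State explicitly how a PCR-confirmed reinfection counts in the ITT proportions.
- Keep the exclusion-based proportions and the competing-risk cumulative incidence as named sensitivity analyses.
- Delete the words that leave the choice between censoring and competing risks open.

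The cost is SAP wording plus one added column, since the per-arm Kaplan-Meier estimates are already planned. The small downside is reliance on censoring at reinfection being independent of recrudescence; the two sensitivity analyses show how far the result depends on how reinfection is handled.

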**Table 2a Comparison of Day 42 PCR corrected Efficacy as proportions of Various ACTs with matching TACTs by sites**

## STATISTICAL ANALYSIS PLAN

Site	PCR corrected ACPR at day 42, n/N, (%)				Risk difference (95% CI, p-value)	
	AL+Placebo (N=XXXX)	AL+AQ (N=XXXX)	ASMQ+Placebo (N=XXXX)	ASMQ + PPQ (N=XXXX)	AL+Placebo vs AL+AQ	ASMQ+Placebo vs ASMQ+PPQ
Burkina Faso	XX/XXX (XX.X)	XX/XXX (XX.X)	XX/XXX (XX.X)	XX/XXX (XX.X)	XX.X (XX.X - XX.X, 0.XXX)	XX.X (XX.X - XX.X, 0.XXX)
DR Congo	XX/XXX (XX.X)	XX/XXX (XX.X)	XX/XXX (XX.X)	XX/XXX (XX.X)	XX.X (XX.X - XX.X, 0.XXX)	XX.X (XX.X - XX.X, 0.XXX)
Gambia	XX/XXX (XX.X)	XX/XXX (XX.X)	XX/XXX (XX.X)	XX/XXX (XX.X)	XX.X (XX.X - XX.X, 0.XXX)	XX.X (XX.X - XX.X, 0.XXX)
Guinea	XX/XXX (XX.X)	XX/XXX (XX.X)	XX/XXX (XX.X)	XX/XXX (XX.X)	XX.X (XX.X - XX.X, 0.XXX)	XX.X (XX.X - XX.X, 0.XXX)
Niger	XX/XXX (XX.X)	XX/XXX (XX.X)	XX/XXX (XX.X)	XX/XXX (XX.X)	XX.X (XX.X - XX.X, 0.XXX)	XX.X (XX.X - XX.X, 0.XXX)
Nigeria	XX/XXX (XX.X)	XX/XXX (XX.X)	XX/XXX (XX.X)	XX/XXX (XX.X)	XX.X (XX.X - XX.X, 0.XXX)	XX.X (XX.X - XX.X, 0.XXX)
Tanzania	XX/XXX (XX.X)	XX/XXX (XX.X)	XX/XXX (XX.X)	XX/XXX (XX.X)	XX.X (XX.X - XX.X, 0.XXX)	XX.X (XX.X - XX.X, 0.XXX)
Rwanda	XX/XXX (XX.X)	XX/XXX (XX.X)	XX/XXX (XX.X)	XX/XXX (XX.X)	XX.X (XX.X - XX.X, 0.XXX)	XX.X (XX.X - XX.X, 0.XXX)
All sites	XX/XXX (XX.X)	XX/XXX (XX.X)	XX/XXX (XX.X)	XX/XXX (XX.X)	XX.X (XX.X - XX.X, 0.XXX)	XX.X (XX.X - XX.X, 0.XXX)

[figure not shown]
[figure not shown]

## STATISTICAL ANALYSIS PLAN

**Figure 3 The difference between TACT vs ACT of Day 42 PCR corrected Efficacy as proportions by site****Table 2b Comparison of Day 42 PCR corrected Efficacy using survival methods of Various ACTs with matching TACTs by sites**

Site	PCR corrected ACPR at day 42, Cumulative recurrent infection free percentage (efficacy), % (95% CI)				Hazard ratio (95% CI, p-value)	
	AL+Placebo (N=XXXX)	AL+AQ (N=XXXX)	ASMQ+Placebo (N=XXXX)	ASMQ + PPQ (N=XXXX)	AL+Placebo vs AL+AQ	ASMQ+Placebo vs ASMQ+PPQ
Burkina Faso	XX.X (XX.X - XX.X)	XX.X (XX.X - XX.X)	XX.X (XX.X - XX.X)	XX.X (XX.X - XX.X)	XX.X (XX.X - XX.X, 0.XXX)	XX.X (XX.X - XX.X, 0.XXX)
DR Congo	XX.X (XX.X - XX.X)	XX.X (XX.X - XX.X)	XX.X (XX.X - XX.X)	XX.X (XX.X - XX.X)	XX.X (XX.X - XX.X, 0.XXX)	XX.X (XX.X - XX.X, 0.XXX)
Gambia	XX.X (XX.X - XX.X)	XX.X (XX.X - XX.X)	XX.X (XX.X - XX.X)	XX.X (XX.X - XX.X)	XX.X (XX.X - XX.X, 0.XXX)	XX.X (XX.X - XX.X, 0.XXX)
Guinea	XX.X (XX.X - XX.X)	XX.X (XX.X - XX.X)	XX.X (XX.X - XX.X)	XX.X (XX.X - XX.X)	XX.X (XX.X - XX.X, 0.XXX)	XX.X (XX.X - XX.X, 0.XXX)
Niger	XX.X (XX.X - XX.X)	XX.X (XX.X - XX.X)	XX.X (XX.X - XX.X)	XX.X (XX.X - XX.X)	XX.X (XX.X - XX.X, 0.XXX)	XX.X (XX.X - XX.X, 0.XXX)
Nigeria	XX.X (XX.X - XX.X)	XX.X (XX.X - XX.X)	XX.X (XX.X - XX.X)	XX.X (XX.X - XX.X)	XX.X (XX.X - XX.X, 0.XXX)	XX.X (XX.X - XX.X, 0.XXX)
Tanzania	XX.X (XX.X - XX.X)	XX.X (XX.X - XX.X)	XX.X (XX.X - XX.X)	XX.X (XX.X - XX.X)	XX.X (XX.X - XX.X, 0.XXX)	XX.X (XX.X - XX.X, 0.XXX)
Rwanda	XX.X (XX.X - XX.X)	XX.X (XX.X - XX.X)	XX.X (XX.X - XX.X)	XX.X (XX.X - XX.X)	XX.X (XX.X - XX.X, 0.XXX)	XX.X (XX.X - XX.X, 0.XXX)
All sites	XX.X (XX.X - XX.X)	XX.X (XX.X - XX.X)	XX.X (XX.X - XX.X)	XX.X (XX.X - XX.X)	XX.X (XX.X - XX.X, 0.XXX)	XX.X (XX.X - XX.X, 0.XXX)

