15. STATISTICAL CONSIDERATIONS

15.1. Sample size justification

These studies will have a non-inferiority trial design. Each site will be powered for the efficacy endpoint. For the safety and tolerability endpoint, the sample size will be pooled across the study

sites to achieve the desired power of at least 80% to detect rare events.

For sample size calculations, the following assumptions have been used: The expected efficacy of ACTs (AL, ASMQ) in these countries is expected to be approximately 96%. The matching TACT efficacy is assumed to be at least 90% under the null hypothesis of inferiority based on the WHO 90% efficacy threshold. However preliminary TRACII study data suggest that TACTs potentially may have a better efficacy of 1% to 2% higher in favour of TACT (i.e. a conservative 97%-98% efficacy or higher).

A one-sided alpha of 0.025 has been used in sample size calculations as non-inferiority is in one direction. For the efficacy outcome, a sample size of 60 subjects in the ACT plus placebo arms and 120 subjects in the matching TACT would be needed to achieve approximately 80% power to detect a non-inferiority margin difference between the group efficacy of -6%. With an additional 20% to cover for loss to follow up, we would therefore need 72 subjects in ACT plus placebo group and 144 subjects in the matching TACT in each of the sites. Since there will be 4 arms, it means we will need 432 subjects per site with 144 subjects in the two ACT arms combined and 288 subjects in the two TACT arms combined.

The sample sizes are in the ratio of 1:2 for ACT vs TACT to allow us to collect more safety and tolerability data for TACTs, which could be beneficial to both policy makers as well as future malaria patients [26, 27]. With these numbers of recruited subjects in Africa, we will have a power above 80% to detect an increase of the incidence of adverse events from 1 in 100 to 3 in 100 for subjects treated with ACT as compared to the matching TACT, respectively.

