**STATISTICAL ANALYSIS PLAN**

Total Bilirubin (µMol/L): median (IQR)	XX.X (XX.X- XX.X)	XX.X (XX.X- XX.X)	XX.X (XX.X- XX.X)	XX.X (XX.X- XX.X)	XX.X (XX.X- XX.X)
Alkaline Phosphatase (IU/L): median (IQR)	XX.X (XX.X- XX.X)	XX.X (XX.X- XX.X)	XX.X (XX.X- XX.X)	XX.X (XX.X- XX.X)	XX.X (XX.X- XX.X)
QT interval on monitor (milliseconds): median (IQR)	XX.X (XX.X- XX.X)	XX.X (XX.X- XX.X)	XX.X (XX.X- XX.X)	XX.X (XX.X- XX.X)	XX.X (XX.X- XX.X)
Calculated QTc Bazett interval (milliseconds): median (IQR)	XX.X (XX.X- XX.X)	XX.X (XX.X- XX.X)	XX.X (XX.X- XX.X)	XX.X (XX.X- XX.X)	XX.X (XX.X- XX.X)

**3.3 Efficacy of the ACTs and TACTs as defined by the 42-day PCR corrected adequate clinical and parasitological response (ACPR) within each individual site**

Efficacy will be reported as cumulative ACPR cure rates by day 42 estimated by day 42 PCR corrected efficacy and compared between ACT vs TACT. The Kaplan Meier/survival methods will be used to visually show time to . Non-inferiority will be assessed using 95% one side confidence intervals.

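### The survival analysis of the primary endpoint (SAP Table 2b) compares arms only by hazard ratio, so it gives no between-arm result that can be read against the -6 point margin

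*SAP*

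**What the plan says.** Protocol 15.1 and SAP 2.2.1 size each site to "detect a non-inferiority margin difference between the group efficacy of -6"%, with one-sided alpha 0.025. This is the only margin in either document, and it is on the scale of an absolute difference in efficacy.

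SAP 3.3 then shows the day-42 PCR-corrected comparison twice:

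- Table 2a (proportions) compares matching arms by "Risk difference (95% CI, p-value"), and Figure 3 plots the TACT versus ACT difference by site.
- Table 2b (survival methods) gives each arm's "Cumulative recurrent infection free percentage (efficacy), % (95% CI") and compares matching arms only by "Hazard ratio (95% CI, p-value"). No difference between the arm-wise estimates is planned. Tables 3b, 4b and 5b have the same layout.

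The role of the survival analysis is described in two ways. SAP 1.1 places it in the ITT strategy: "Furthermore, the estimates of efficacy using survival analysis will be done", with the reason that "This approach will help in handling missing data as all patients will be included in the analysis and censored at their last follow-up time". SAP 3.3 gives it a lesser role, in a sentence that breaks off: "The Kaplan Meier/survival methods will be used to visually show time to". The decision rule in 3.3 is "Non-inferiority will be assessed using 95% one side confidence intervals", and it does not say on which scale.

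Neither document gives a hazard-ratio margin, a null value for the hazard-ratio p-value, or a method for an arm with no failures.

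**The concern.** The ITT proportions in Table 2a are complete-case, and the design allows 20% for loss to follow-up. The survival analysis is the planned check that keeps the patients whom Table 2a leaves out. For that purpose its between-arm result should be comparable with the Table 2a result and with the margin. A hazard ratio without a margin is not.

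Two practical consequences follow. First, a hazard-ratio p-value with no stated null will be read as a test of equality, and with few failures a non-significant result says little about non-inferiority. Second, the ordinary Cox estimate goes to zero or infinity when one arm has no failures, and there is nothing to estimate when neither arm has any. Failures are expected to be few at each site, so some cells of Table 2b may not be fillable as planned.

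**Working it through.** **Inputs** (Protocol 15.1, SAP 2.2.1): ACT efficacy 96%; TACT efficacy 97 to 98% or higher, with 96% (equal efficacy) added here as a lower case; margin -6 points; one-sided alpha 0.025; 60 ACT and 120 TACT evaluable per pair, 72 and 144 randomised. There are 8 AL pairs and 7 ASMQ pairs (Rwanda has no ASMQ arms), so 15 site-level pairs.

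**1. The plan's own figure.** Unpooled normal approximation at TACT 98%: SE = sqrt(0.96×0.04/60 + 0.98×0.02/120) = 0.0283; (0.02 + 0.06)/0.0283 - 1.96 = 0.86; power 0.806. The stated figure of about 80% with 60/120 is reproduced. At TACT 97% the same formula gives 0.654, and at 96% it gives 0.491.

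**2. Could the hazard ratio be read against -6 points by conversion?** Under proportional hazards the equivalent margin is ln(ACT - 0.06)/ln(ACT):

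| ACT efficacy | Equivalent HR margin |
|---|---|
| 95% | 2.27 |
| 96% | 2.58 |
| 97% | 3.10 |
| 98% | 4.13 |

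No single hazard-ratio limit stands for -6 points, because the value moves with the control efficacy at each site. This is a reason to report the difference, not to add a hazard-ratio margin.

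**3. Arms with no failures.** P(no failures) = efficacy^n in each arm; P(at least one such arm) = 1 - (1 - P_ACT)(1 - P_TACT); over 15 pairs, taken as independent, 1 - (1 - P)^15. For example, at TACT 98% with 60/120: 0.96^60 = 0.086, 0.98^120 = 0.089, either arm 0.167.

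| n (ACT/TACT) | TACT efficacy | Expected failures ACT, TACT | Either arm zero | At least 1 of 15 pairs | Expected pairs of 15 |
|---|---|---|---|---|---|
| 60/120 | 96% | 2.4, 4.8 | 9.3% | 77% | 1.4 |
| 60/120 | 97% | 2.4, 3.6 | 11.0% | 83% | 1.7 |
| 60/120 | 98% | 2.4, 2.4 | 16.7% | 94% | 2.5 |
| 72/144 | 96% | 2.9, 5.8 | 5.6% | 58% | 0.8 |
| 72/144 | 97% | 2.9, 4.3 | 6.5% | 63% | 1.0 |
| 72/144 | 98% | 2.9, 2.9 | 10.5% | 81% | 1.6 |

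The survival analysis includes censored patients, so its risk lies roughly between the two blocks.

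**4. What the p-value would show.** If TACT efficacy were truly 90%, exactly at the margin, with 60/120 evaluable, a Wald test of HR = 1 is non-significant in about 92% of the estimable comparisons. A Newcombe 95% interval for the difference, read against -6 points, declares non-inferiority in 2.8%.

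**5. What a difference would deliver.** The day-42 Kaplan-Meier difference with a Greenwood 95% CI was simulated with 72/144 randomised and 16.7% censored (assumed; 12/72 is the loss that takes 72 to 60). Power against -6 points is about 0.56, 0.78 and 0.93 at TACT 96%, 97% and 98%. With 0 to 30% censoring the ranges are 0.53 to 0.59, 0.73 to 0.80 and 0.91 to 0.94. These are slightly optimistic, because Greenwood gives zero variance to an arm without failures.

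**6. An interval that survives zero failures.** The Wilson lower limit for n successes out of n is n/(n + 1.96²). For 120 of 120 it is 120/123.84 = 96.9%. With no failures in either arm (60 of 60 and 120 of 120), the observed efficacy is 100% in both, so the Newcombe lower limit for TACT minus ACT is -sqrt((1 - 0.969)² + 0²) = -3.1 points. This is finite and can be read against -6.

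**The case against.** The strongest reply is that the hazard ratio is not asked to decide anything. SAP 1.1 makes the ITT complete-case analysis the main strategy and adds survival after it; SAP 3.3 speaks of showing time to event visually; Table 2a and Figure 3 are on the margin's scale. A reader might infer that the plan cannot answer its non-inferiority question. The documents do not support that: Table 2a answers it.

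Table 2b also prints each arm's Kaplan-Meier efficacy with its CI, so the point difference is a subtraction away. This is true, but its interval is not planned, and the interval is what must be read against the margin.

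A reader might also infer that empty arms will be the norm. With ACT at 98% and TACT at 99% the chance is 50.8% per pair, but 98% for ACT is not a planning assumption. On the stated figures most site-level hazard ratios are estimable. In the all-sites row the AL+placebo arm alone expects about 19 failures (8 × 2.4).

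Poor power of a hazard-ratio non-inferiority test would be no defect either, since the SAP plans no such test. The risk of misreading a p-value is not special to Table 2b, because Table 2a carries an unlabelled p-value too. Finally, the documents give no margin for day 63, so -6% cannot simply be carried over to Table 3b.

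These points limit the concern to a supportive analysis. They do not supply a between-arm survival result on the margin's scale or a rule for empty arms.

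**Conclusion.** The point holds as a cheap improvement to a supportive analysis, not as a flaw in the primary decision. Table 2b, the ITT analysis that keeps all randomised patients, gives no between-arm result that can be set against -6 points, so it cannot formally confirm or question the non-inferiority finding of Table 2a when patients are missing. The Cox estimate fails in 9.3 to 16.7% of site-level pairs at 60/120 (5.6 to 10.5% at 72/144). The chance of meeting this at least once in 15 pairs is 58 to 94%.

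The figures rest on ACT efficacy of 96%, TACT efficacy of 96 to 98%, independent pairs, all 15 pairs being run, and an ordinary Cox model. Penalised or profile-likelihood methods could handle one empty arm, but none is planned. The p-value is taken as the usual test of HR = 1 because the SAP states no other null.

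**What to change.** In Table 2b, add as the main survival comparison the day-42 difference TACT minus ACT in Kaplan-Meier efficacy, with a two-sided 95% CI (matching one-sided alpha 0.025) whose lower limit is read against -6%. The one-sided 95% wording in SAP 3.3 should be aligned with that alpha at the same time.

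- **Estimator.** SAP 3.3 leaves open whether reinfections are censored or treated as competing risks. State which in advance. If they are competing risks, use the difference in 1 minus cumulative incidence and its own variance.
- **Interval.** Use one defined with zero failures, for example a Newcombe/MOVER interval from arm-wise Wilson limits. With failures, take the effective sample size as S(1 - S)/Greenwood variance, where S is the day-42 estimate. With none, that ratio is 0/0, so set it to a prespecified count such as the number at risk at day 42.
- **Hazard ratio.** Keep it as descriptive where both arms have failures, name the reference arm, and mark other cells as not estimable.
- **Table 3b.** Report the day-63 difference with its CI, without applying -6% unless the sponsor states a margin for day 63.

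The cost is one extra column, a short SAP paragraph and a few lines of code. No new data are needed.
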